Section 3.7.1.1.2.4, Conversion to Oral Brexpiprazole (Conversion Weeks 1, 2, 3, and 4 of Phase A)	Conversion Week 4/Baseline of Phase B:  Blood samples for clinical laboratory tests (hematology, coagulation parameters, and serum chemistry, including prolactin, HbA1c, ACTH, cortisol, and TSH with reflex to T4 if the result for TSH is abnormal) must be collected after a minimum 8-hour fast.	Conversion Week 4/Baseline of Phase B:  Blood samples for clinical laboratory tests (hematology, coagulation parameters, and serum chemistry, including prolactin, HbA1c, and TSH with reflex to T4 if the result for TSH is abnormal) must be collected after a minimum 8-hour fast.
Section 3.7.1.2.1, Week 1	Not applicable (newly added text)	
Section 3.7.1.2.2, Week 2	Not applicable (newly added text)	

C

Version 2.0, 20 Oct 2017

Protocol 331-201-00083

Section 3.7.1.2.3, Week 4	Urine will be collected from all subjects for urinalysis and urine screen(s) for drugs of abuse.	Urine will be collected from all subjects for urine screen(s) for drugs of abuse.
Section 3.7.1.2.3, Week 4	Not applicable (newly added text)	Ç.
Section 3.7.1.2.4, Week 8	Not applicable (newly added text)	CCI
Section 3.7.1.2.5, Week 12	Not applicable (newly added text)	
Section 3.7.1.2.6, Week 18	Not applicable (newly added text)	C
Section 3.7.1.2.7, End of Treatment - Week 26/Early Termination	Not applicable (newly added text)	C-
Section 3.7.1.3	Adverse events and concomitant medications will be recorded and a confirmation of data download from the wearable device will be performed.	Adverse events and concomitant medications will be recorded.
CCI		

Protocol 331-201-00083

Section 3.7.2.4, Other Assessments	Not applicable (newly added text)	CCI
Table 3.7.3.2-1, Clinical Laboratory Assessments	Adrenocorticotropic hormone (ACTH) Cortisol	Assessments removed.
Section 4.2, Other Restrictions	Not applicable (newly added text)	Anticholinergics are permitted for the treatment of EPS up to a maximum of 4 mg/day benztropine or its equivalent and propranolol is permitted for akathisia or tremor up to a maximum of 20 mg 3 times daily (total of 60 mg/day). Sites should only utilize medications that are approved for these indications in their respective countries.
Section 5.1, Definitions	Pregnancies are also defined as IREs. Although normal pregnancy is not an AE, it will mandate IMP discontinuation and must be reported on an IRE form to the sponsor. Pregnancy will only be documented on the AE ePlatform if there is an abnormality or complication.	Pregnancies are also defined as IREs. Although normal pregnancy is not an AE, it will mandate IMP discontinuation and must be reported on the clinical trial pregnancy and breastfeeding form, or other designated form, to the sponsor. Pregnancy will only be documented on the AE ePlatform if there is an abnormality or complication.
Sction 5.2, Eliciting and Reporting Adverse Events	To avoid bias in eliciting AEs, subjects should be asked the non-leading question: "How have you felt since your last visit?" All AEs (serious and nonserious) reported by the subject must be recorded on the eSource and ePlatform provided by the sponsor.	To avoid bias in eliciting AEs, subjects should be asked the non-leading question: "How have you felt since your last visit?" All AEs (serious and nonserious) reported by the subject must be recorded on the eSource platform provided by the sponsor.

140

Protocol 331-201-00083

Section 7.5, Analysis of Demographic and Baseline Characteristics	Baseline demographic characteristics including age, race, ethnicity, gender, weight, height, and body mass index (BMI) for the randomized subjects will be summarized by descriptive statistics (frequency, mean, median, standard deviation, maximum, minimum, and percentage when applicable).	Baseline demographic characteristics including age, race, ethnicity, gender, weight, height, and body mass index (BMI) will be summarized by descriptive statistics (frequency, mean, median, standard deviation, maximum, minimum, and percentage when applicable).
	Baseline disease severity and psychiatric history will also be summarized by descriptive statistics for the Safety Sample to identify any potential lack of balance between the treatment groups.	
Section 7.6.3, Electrocardiogram Data	Mean change from baseline will be summarized by treatment group and by visit.	Mean change from baseline will be summarized by visit.
	The incidence of clinically relevant changes will be calculated for ECG parameters and summarized by treatment group and by visit.	The incidence of clinically relevant changes will be calculated for ECG parameters and summarized by visit.
CCI		
Appendix 5, Criteria for Identifying Laboratory Values of Potential Clinical Relevance	Laboratory test criteria updated to match	h text of the protocol.
CCI		

- Protocol number: 331-201-00083
- Document title: A Multicenter, Open-label Trial to Evaluate the Safety and Tolerability of Brexpiprazole in the Treatment of Subjects with Bipolar I Disorder
- Version number: 2.0
- Date of the document: 17 July 2019
- NCT number: NCT03287869

Otsuka Pharmaceutical Development & Commercialization, Inc.

Investigational New Drug

Brexpiprazole (OPC-34712)

A Multicenter, Open-label Trial to Evaluate the Safety and Tolerability of Brexpiprazole in the Treatment of Subjects with Bipolar I Disorder

Protocol No. 331-201-00083 IND No. 134115 EudraCT No. 2017-002225-38

Statistical Analysis Plan

Version: Final

Date: July 10, 2019

CONFIDENTIAL - PROPRIETARY INFORMATION

Confidential

May not be used, divulged, published or otherwise disclosed
without the consent of Otsuka Pharmaceutical Development & Commercialization, Inc.

Confidential - Proprietary Information

1

Table of Contents

1 abi	e of Contents2
1	Introduction4
2	Study Objectives 4
3	Trial Details4
3.1	Study Design4
3.2	Trial Treatments
4	Sample Size and Power Justification8
5	Data Sets for Analysis and Missing Data
5.1	Data Sets for Analysis
5.2	Handling of Missing Data8
6	Study Conduct
6.1	Subject Disposition, Completion Rate and Reasons for Discontinuation 8
6.2	Treatment Compliance 9
7	Baseline Characteristics9
7.1	Baseline Definition 9
7.2	Demographic Characteristics9
7.3	Baseline Psychiatric Evaluation
8	Efficacy Analysis9
9	Safety Analysis11
9.1	Adverse Events 12
9.2	Clinical Laboratory Tests
9.2.1	Drug Induced Liver Injury (DILI)
9.2.2	Metabolic Change
9.3	Physical Examination and Vital Signs Data
9.4	12-Lead ECG
CCI	16
9.6	Concomitant Medications
9.7	Extent of Exposure17
CCI	17
Confid	lential - Proprietary Information 2 10 July 20

10	Conventions	17
CCI		
CCI		
CCI		
CCI		
11	Potential Clinical Relevance Criteria from Protocol	22
12	Proposed List of Summary Tables	25

1 Introduction

This statistical analysis plan (SAP) documents the statistical methodology and data analysis algorithms and conventions to be applied for statistical analysis and reporting of efficacy and safety data of study 331-201-00083. All amendments to the protocol are taken into consideration in developing this SAP.

2 Study Objectives

The purpose of this trial is to assess the safety and tolerability of brexpiprazole (OPC-34712) in the treatment of subjects with bipolar I disorder.

3 Trial Details

3.1 Study Design

This is a multicenter, open-label trial designed to assess the safety and tolerability of oral brexpiprazole (OPC-34712) (2-4 mg/day) as treatment in adults with bipolar I disorder. The trial will be conducted on an outpatient basis. Enrollment into the trial will be drawn from eligible subjects who will include subjects who completed the 3-week treatment in the double-blind, phase 3 efficacy trials (ie, Trials 331-201-00080 or 331-201-00081) and, in the investigator's judgment, could potentially benefit from treatment with oral brexpiprazole (OPC-34712) for bipolar I disorder. In the event the sponsor determines that the enrollment rate of rollover subjects will not be sufficient to meet the target completion of approximately 175 subjects at 6 months, de novo subjects may be enrolled at select sites. The enrollment of de novo subjects at any site will not be permitted until initiation and notification by the sponsor.

The trial will be organized as follows:

Rollover Subjects:

Screening/Baseline: Subjects who completed Day 21 of the double-blind trial and had no major protocol deviation will be screened for eligibility at the last visit of the double-blind trial (i.e., Week 3 [Day 21] visit of Trials 331-201-00080 or 331-201-00081). Subjects will sign a separate informed consent form (ICF) for participation in Trial 331-201-00083 before any procedures specific to the open-label trial are performed. The assessments from the last visit of the double-blind trial will serve as the baseline measures for Trial 331-201-00083 for any assessment that is not unique to the open-label trial. Medical history will be updated, if necessary.

Confidential - Proprietary Information

4

Open-label Treatment Phase: Eligible subjects from Trials 331-201-00080 or 331-201-00081 will receive 26 weeks of daily treatment with open-label brexpiprazole (OPC-34712) (2-4 mg/day) in open-label treatment phase of Trial 331-201-00083, as described in Section 3.2. Visits will occur at the end of Weeks 1, 2, 4, 8, 12, 18, and 26.

Follow-up: Subjects will be followed up for safety via telephone contact or clinic visit 21 (± 2) days after the last dose of open-label investigational medicinal product (IMP).

De Novo Subjects

There are no de novo subjects enrolled in the study.

See Figure 3.1-1 for schematics of the trial design for rollover subjects.

[figure not shown]

Figure 3.1-1 Trial Design Schematic - Rollover Subjects

Confidential - Proprietary Information

6

3.2 Trial Treatments

Rollover Subjects

- The first dose of open-label brexpiprazole (OPC-34712) will be taken one day after the last dose of double-blind IMP is taken in Trials 331-201-00080 or 331-201-00081 so that treatment continues without interruption. It is anticipated that the last dose of the double-blind, phase 3 efficacy trial will be taken the day of the Day 21 (Week 3) visit of Trial 331-201-00080 or 331-201-00081 (ie, the day of the screening/baseline visit for the open-label trial).
- All subjects will start on 2 mg/day of brexpiprazole (OPC- 34712) regardless of treatment assignment in the double-blind trial.

All subjects will receive a starting dose of 2 mg/day of brexpiprazole from Days 1 to 3, followed by titration to 3 mg/day brexpiprazole on Day 4. Subjects may be titrated (or retitrated) to a higher dose of brexpiprazole, up to a maximum of 4 mg/day, based on treatment response and at the investigator's discretion anytime at Day 7 or thereafter. Subjects who are unable to tolerate their current dose can be titrated down at any time to a minimum of 2 mg/day. Dose adjustments must be made in increments of 1 mg/day. Subjects who are unable to tolerate 2 mg/day brexpiprazole will be discontinued from the trial.

The dosing strategy is summarized in Table 3.2.2.1-1. Subjects must return to the clinic for unscheduled visits if dose adjustments for brexpiprazole are required between scheduled visits. Dose adjustments must ultimately be made based upon the clinical judgment of the investigator as it relates to tolerability and therapeutic response. All doses of brexpiprazole should be taken orally once daily and can be administered without regard to meals. Subjects are to take IMP at approximately the same time each day.

Table 3.2.2.1-1 Dosing Schedule - Open-label Treatment Phase			
	Trial Visit		
IMP	Days 1-3	Day 4 ^a	Day 7-Week 26
Brexpiprazole (OPC-34712)	2 mg/day	3 mg/day	2-4 mg/day ^b

^aDown titration can occur at any time due to tolerability after Day 4. The minimum dose allowed is 2 mg/day.

Confidential - Proprietary Information

7

^bOption to titrate to 2 to 4 mg (ie, 2 mg, 3 mg, or 4 mg) based on clinical response and tolerability; changes must occur in 1 mg/day increments. Increases up to 4 mg/day may occur no earlier than Day 7.

4 Sample Size and Power Justification

[figure not shown]
The sample size is not based on statistical power considerations but on ICH/GCP requirements. The trial population will be derived from eligible subjects from the double-blind, phase 3 trials (ie, Trials 331-201-00080 and 331-201-00081). In the event the sponsor determines that the enrollment rate of rollover subjects will not be sufficient to meet the target completion of approximately 175 subjects at 6 months, de novo subjects may be enrolled at selected sites. The enrollment of de novo subjects at any site will not be permitted until initiation and notification by the sponsor.

5 Data Sets for Analysis and Missing Data

5.1 Data Sets for Analysis

The following datasets are defined for this trial:

- Enrolled Sample, which comprises all subjects who sign an ICF for the trial.
- Safety Sample, which comprises all subjects who will receive at least 1 dose of IMP.

6 Study Conduct

There are no de novo subjects enrolled in the study.

6.1 Subject Disposition, Completion Rate and Reasons for Discontinuation

Subject disposition will be summarized for the Enrolled Sample by parent study treatment group for rollover subjects and overall.

Confidential - Proprietary Information

8

Subject completion rate and reasons for discontinuation will be summarized for the Enrolled Sample by parent study treatment group for rollover subjects and overall.

6.2 Treatment Compliance

Based on the Investigational medicinal product (IMP) panel of the CRF, compliance in taking IMP is calculated by dividing the number of tablets/capsules taken by the total number of tablets/capsules the patients were scheduled to take during the study period. For lost-to-follow up patients, last IMP end date record will be used as the treatment end date.

[figure not shown]
7 Baseline Characteristics

7.1 Baseline Definition

Baseline is defined as the last available measurement prior to the first dose of open-label IMP in the open-label treatment phase.

[figure not shown]
7.2 Demographic Characteristics

Baseline demographic characteristics including age, race, ethnicity, gender, weight, height, and body mass index (BMI) will be summarized by descriptive statistics (frequency, mean, median, standard deviation, maximum, minimum, and percentage when applicable) for the Enrolled Sample by parent study treatment group for rollover subjects and overall.

Confidential - Proprietary Information

9

[figure not shown]

Until the information herein is released by Otsuka to the public domain, the contents of this document are Otsuka confidential information and should not be duplicated or re-distributed without prior written consent of Otsuka.

10

10 July 2019

Confidential - Proprietary Information

9 Safety Analysis

The primary safety endpoint analysis is the frequency and severity of AEs in the open-label treatment phase (see Section 9.1). Other standard safety variables to be analyzed include clinical laboratory tests, vital signs, body weight, waist circumference, BMI, 12-lead electrocardiograms (ECGs), and physical examinations.

Safety analyses will be conducted based on the Safety Sample, and summary statistics will be provided by parent study treatment group for rollover subjects and overall, unless otherwise indicated.

Unless otherwise specified, in general, analysis of safety data will be performed on observed case and for last visit.

9.1 Adverse Events

All adverse events will be coded by System Organ Class (SOC) and Preferred Term (PT) according to the Medical Dictionary for Regulatory Activities (MedDRA). AEs that are sexspecific, e.g., ovarian cancer, will have their incidence rates evaluated for the specific sex.

Treatment-emergent AEs (TEAEs) are defined as AEs with an onset date on or after the first dose of IMP. In more detail, TEAEs are all adverse events which started after start of IMP; or if the event was continuous from baseline and was worsening, serious, study drug related, or resulted in death, discontinuation, interruption or reduction of study therapy. Adverse events occurring up to 21 days after the last day of IMP will be included in the summary tables.

The incidence of the following events in the open-label treatment phase will be summarized using the Safety Sample:

- a) TEAEs
- b) TEAEs by severity
- c) TEAEs potentially causally related to the IMP
- d) TEAEs with an outcome of death
- e) Serious TEAEs
- f) TEAEs leading to discontinuations of the IMP

The above summaries (b), (e) and (f) will also be prepared for TEAEs potentially causally related to the IMP.

In addition, incidence of TEAE during the open-label treatment phase of at least 5% by SOC and PT will be provided.

Incidence of TEAEs by SOC and PT will be summarized for sex, race, age and region subgroups.

EPS-related AEs will be grouped into five categories.

- 1) Dystonic Events, which include cervical spasm, dystonia, emprosthotonos, muscle contractions involuntary, muscle rigidity, muscle spasms, muscle spasticity, myotonia, nuchal rigidity, oculogyration, opisthotonos, pleurothotonus, risus sardonicus, torticollis, and trismus;
- 2) Parkinsonian Events, which include akinesia, asterixis, athetosis, bradykinesia, cogwheel rigidity, essential tremor, extrapyramidal disorder, freezing phenomenon, gait festinating, hyportonia, hypokinesia, hypokinesia neonatal, intention tremor, masked facies, parkinson's

Confidential - Proprietary Information

disease, parkinsonian crisis, parkinsonian gait, parkinsonian rest tremor, parkinsonism, tremor, and tremor neonatal;

- 3) Akathisia Events, which include akathisia, hyperkinesia, and psychomotor hyperactivity;
- 4) Dyskinetic Events, which include ballismus, buccoglossal syndrome, choreoathetosis, clumsiness, dyskinesia, dyskinesia neonatal, dyskinesia oesophageal, fumbling, nodding of head, on and off phenomenon, and tardive dyskinesia;
- 5) Residual Events, which include chorea, huntington's chorea, muscle twitching, and myoclonus.

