Investigational Medicinal Product(s), Dose, Dosage regimen, Treatment period, Formulation, Mode of Administration:	All subjects will receive a starting dose of 2 mg/day of brexpiprazole from Days 1 to 3, followed by titration to 3 mg/day brexpiprazole on Day 4. Subjects may be titrated (or re-titrated) to a higher dose of brexpiprazole, up to a maximum of 4 mg/day, based on treatment response and at the investigator's discretion anytime at Day 7 or thereafter. Subjects who are unable to tolerate their current dose can be titrated down at any time to a minimum of 2 mg/day. Dose adjustments must be made in increments of 1 mg/day. Subjects who are unable to tolerate 2 mg/day brexpiprazole will be discontinued from the trial.
	Subjects experiencing tolerability issues in-between visits may have their doses adjusted at any time during an unscheduled in-clinic visit.
Trial Assessments:	CCI
	Pharmacokinetic: None.
	Safety: Adverse event (AE) reporting, clinical laboratory tests, 12-lead electrocardiogram (ECG), vital signs, waist circumference, physical examination,
	Screening/Other: Medical, psychiatric, and medication history, urine drug and alcohol screening, serum pregnancy test, and MINI.
Criteria for Evaluation:	Primary Endpoint: The primary endpoint is the safety and tolerability of brexpiprazole (OPC-34712), as assessed by the frequency and severity of AEs.
	CCI

Confidential - Proprietary Information

Version 2.0, 20 Oct 2017

3

Confidential - Proprietary Information

4

be coded using the Medical Dictionary for Regulatory Activities (MedDRA) preferred term. The incidence of treatment-emergent adverse events (TEAEs) will include the following summaries:

- TEAEs by severity
- Potentially drug-related TEAEs
- TEAEs with an outcome of death
- Serious TEAEs
- Discontinuations due to TEAEs

A TEAE is defined as an AE that starts after the first dose of investigational medicinal product (IMP) or an AE that is reported at baseline and increases in intensity or becomes serious or trial drug-related or results in death, discontinuation, interruption, or reduction of IMP.

Descriptive statistics will be provided for each endpoint, and will be summarized at each trial visit using the observed cases (OC) dataset and at the last visit using the last observation carried forward (LOCF) dataset. Baseline is defined as the last available measurement prior to the first dose of open-label IMP in the open-label treatment phase.

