## 7.4 Primary and Secondary Endpoint Analyses

# 7.4.1 Primary Endpoint Analysis

The primary safety endpoint analysis is the frequency and severity of AEs in the open-label treatment phase (Phase B). All AEs will be coded using the Medical Dictionary for Regulatory Activities (MedDRA) preferred term. The incidence of TEAEs will include the following summaries:

- TEAEs by severity
- Potentially drug-related TEAEs
- TEAEs with an outcome of death
- Serious TEAEs
- Discontinuations due to TEAEs

A TEAE is defined as an AE that starts after the first dose of IMP or an AE that is reported at baseline and increases in intensity or becomes serious or trial drug-related or results in death, discontinuation, interruption, or reduction of IMP.

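### SAP 9.1 counts an AE continuous from baseline as treatment-emergent if it was serious or drug-related, where protocol 7.4.1 requires that it becomes so

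*SAP*

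**What the plan says.** The protocol states its rule for pre-existing events twice. Section 7.4.1 counts "an AE that is reported at baseline and increases in intensity or becomes serious or trial drug-related", or one that results in death, discontinuation, interruption or reduction of IMP. The synopsis has the same rule, covering AEs that start after the "first dose of investigational medicinal product (IMP) or an AE that is reported at baseline and increases in intensity or becomes serious".

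SAP 9.1 gives two sentences. The first is short: "Treatment-emergent AEs (TEAEs) are defined as AEs with an onset date on or after the first dose of IMP". The second elaborates: "In more detail, TEAEs are all adverse events which started after start of IMP". It then adds events "if the event was continuous from baseline and was worsening, serious, study drug related, or resulted in death", followed by discontinuation, interruption or reduction of study therapy.

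This definition feeds six listed summaries: (a) TEAEs, (b) by severity, (c) potentially related to IMP, (d) with outcome of death, (e) serious, and (f) leading to discontinuation of IMP. The SAP adds: "The above summaries (b), (e) and (f) will also be prepared for TEAEs potentially causally related to the IMP".

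SAP section 1 says that protocol amendments were taken into account. The visible part of the amendment log in protocol Appendix 14 shows no change to the TEAE definition, and the visible SAP text does not mention one.

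**The concern.** The protocol's *becomes* requires something to happen after baseline. The SAP's *was* requires only that the event has the attribute. An event that was serious before the first open-label dose, continued unchanged and had no listed consequence is not a TEAE under the protocol but is one under the SAP as written.

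The frequency and severity of AEs is the trial's only primary endpoint (protocol 3.5.1, 3.5.2; SAP section 9). The sentence at issue decides which events enter its tables. A programmer who follows the SAP literally would attribute to open-label treatment some events that preceded it and did not change under it. The rollover design makes this relevant: subjects move from double-blind to open-label dosing without a gap, and results are shown by parent-study treatment group.

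**Working it through.** No figure in the documents depends on this point, so there is nothing to reproduce. The check compares the two rules over every pattern that an AE ongoing at the first open-label dose can take.

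**Which dose is meant.** I read IMP in the TEAE definition as open-label IMP. SAP 7.1 defines baseline as "the last available measurement prior to the first dose of open-label IMP in the open-label treatment phase", and SAP 3.1 and 9.7 are consistent with this.

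**What already related can mean.** Protocol 5.1 defines relatedness as a reasonable possibility of a temporal and causal link between the IMP and the AE. If that is open-label IMP, no event can be related before the first open-label dose; a later judgement of related means that it became related, which both rules count. The already-related level exists only if relatedness to double-blind IMP also counts. SAP 9.1 says study drug, and SAP 3.2 applies the term IMP to the double-blind product as well, so the text leaves this open. Both cases are shown.

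**Rules.**
- Protocol: count if the event worsens, or has a listed consequence, or becomes serious, or becomes related.
- SAP: count if the event worsens, or has a listed consequence, or is serious at any time, or is related at any time.

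**Case A, relatedness to open-label IMP only.** Worsens (no/yes) × consequence (no/yes) × serious (never/already/becomes) × related (never/becomes) = 2 × 2 × 3 × 2 = 24 patterns.
- Protocol omits: no worsening, no consequence, serious never or already, related never = 2. It counts 24 − 2 = 22.
- SAP omits: none of the four = 1. It counts 24 − 1 = 23.
- Difference: 23 − 22 = 1 pattern (already serious, otherwise unchanged).

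**Case B, relatedness to double-blind IMP also counts.** 2 × 2 × 3 × 3 = 36 patterns.
- Protocol omits 2 × 2 = 4 (serious never or already; related never or already). It counts 36 − 4 = 32.
- SAP omits 1. It counts 36 − 1 = 35.
- Difference: 35 − 32 = 3 patterns.

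In both cases every pattern that differs is counted by the SAP only.

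| Unchanged event | Arises in | Listed summaries it can enter | Related-only versions |
|---|---|---|---|
| Already serious | A and B | (a), (b), (e) | none |
| Already related | B only | (a), (b), (c) | (b) |
| Already both | B only | (a), (b), (c), (e) | (b), (e) |

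That is 3 of 6 listed summaries in Case A and 4 of 6 in Case B. Summaries (d) and (f) are not exposed, because both rules count death and discontinuation.

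**How many subjects.** AE recording begins at consent for this trial (protocol 3.7.1.1.1), at the parent-study Day 21 visit. That is the anticipated day of the last double-blind dose, and open-label dosing starts one day after that dose (SAP 3.2). The documented pre-dose window is therefore about one day. The visible text does not say whether older ongoing AEs from the parent trial are entered as AEs here. No count can be derived.

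**The case against.** The strongest reply is that the SAP sentence is shorthand. It opens by elaborating a definition of treatment emergence, and a reader who knows the protocol would supply the missing change. The SAP's conventions section is largely not visible and might hold the derivation rule. This may describe the intent, but it does not remove the conflict. The elaborating sentence is the most detailed rule in view, it omits the change requirement for these two attributes, and it does not defer to the protocol.

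A second reply is that the affected set is nearly empty. In Case A it needs a serious event that is recorded after consent, is ongoing at a first dose anticipated one day later, never worsens and has no listed consequence. This stands as a limit on size. Subjects still in hospital at Day 21 may enrol (inclusion criterion 8), so such an event is conceivable. But protocol 5.2 restricts when exacerbation of the underlying condition is reported as an AE, so their presence supplies no count.

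Three stronger readings are tempting and are not supported:
- A reader might infer that the drug-related tables are certainly inflated. They are exposed only in Case B, which the documents do not settle.
- A reader might take 1 of 24 or 3 of 36 as a rate. These are counts of logical patterns, not of subjects or events.
- A reader might conclude that the SAP can never count fewer events than the protocol. The enumeration covers only events ongoing at the first dose. It does not test the protocol's *reported at baseline* against the SAP's *continuous from baseline*.

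**Conclusion.** The conflict in wording is real and should be corrected. Its certain extent, with IMP read as open-label IMP, is one kind of event: already serious before the first open-label dose and unchanged afterwards, entering summaries (a), (b) and (e). Its conditional extent, if relatedness to double-blind IMP counts, adds unchanged already-related events, which reach (c) and the related-only version of (b). Where such an event is also serious, it reaches (e) and the related-only version of (e) as well.

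The number of subjects is unknown and may be zero. There is no powered hypothesis, so no test or error rate is affected. The reason to act is that an unannounced departure from the protocol sits in the definition behind the only primary endpoint. On worsening and on the listed consequences the two documents agree in substance. Confidence is high on the wording and low on any practical effect.

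**What to change.** In SAP 9.1, replace the words from *worsening* to *study drug related* (with the verb before them) by a change condition: after the first dose of open-label IMP, the event increased in intensity, became serious or became study drug related. Keep the consequences (death, discontinuation, interruption or reduction) as they are. State whether relatedness to double-blind IMP counts. If the sponsor prefers the status rule, the SAP should say that it departs from protocol 7.4.1 and why.

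As a separate clean-up, reconcile the onset wordings. SAP 9.1 uses both on-or-after the first dose and started after start of IMP, while the protocol says that the AE starts after the first dose. On-or-after should not be described as matching 7.4.1.

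The cost is one clause of SAP text and the matching TEAE derivation. It needs no data beyond what the protocol's definition already requires.
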